8. REMOVAL AND REPLACEMENT OF SUBJECTS

Removal of Subjects

Subjects have the right to withdraw fully or partially from the study at any time and for any reason without prejudice to his or her future medical care by the physician or at the institution. The Principal Investigator and REMD Biotherapeutics also have the right to withdraw a subject from the study at any time for any reason.

Withdrawal of full consent for a study means that the subject does not wish to receive further investigational treatment and does not wish to or is unable to continue further study participation. Any subject may withdraw full consent to participate in the study at any time during the study. The Principal Investigator will discuss with the subject the most appropriate way to withdraw to ensure the subject's health.

Withdrawal of partial consent means that the subject does not wish to take investigational product any longer but is still willing to collaborate in providing further data by continuing on study (e.g., participate in all subsequent study visits or procedures). Subjects may decline to continue receiving investigational product at any time during the study. These subjects, as well as those who have stopped receiving investigational product for other reasons (e.g., Principal Investigator or sponsor concern) should continue the schedule of study observations.

Subjects who early terminate the study during the 12-week treatment period will be monitored for 12-weeks after the last injection of study drug (REMD-477 or placebo).

The reason for withdrawal will be recorded on the end-of-study eCRF page. If the subject is withdrawn due to an adverse event, the Principal Investigator will arrange for the subject to have follow-up visits until the adverse event has resolved or stabilized.

Reasons for removal from investigational product or observation might include:

- withdrawal of consent
- administrative decision by the investigator or REMD Biotherapeutics
- pregnancy (report on Pregnancy Notification Worksheet)
- pregnancy in female partner of a male subject during treatment and up to EOS (report on Pregnancy Notification Worksheet)
- ineligibility
- significant protocol deviation

- subject noncompliance
- adverse event (may include disease progression; report on adverse event eCRF)

Replacement of Subjects

Randomized subjects who do not receive REMD-477 or matching placebo may be replaced.

Subjects who receive study drug and do not complete all study procedures as per protocol may be replaced. A replacement subject will be assigned the same dose, route, and treatment group of the replaced subject. However, subjects who are removed from the study as a result of investigational drug related or possibly related adverse events (after receiving study medication) may or may not be replaced, per Investigator's discretion.

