5. SUBJECT ENROLLMENT

Before subjects may be entered into the study, REMD Biotherapeutics, Inc. requires a copy of the site's written IRB approval of the protocol, informed consent form (ICF), and all other subject information and/or recruitment material, if applicable. A subject is considered enrolled once the subject is randomized. However, if a subject has been randomized and does not receive study drug, the subject may be replaced. All subjects must personally sign and date the informed consent form, before any study specific procedures are performed.

All subjects who enter into the screening period for the study (defined as the point at which the subject signs the informed consent) will receive a unique subject identification number before any study procedures are performed. This number will be used to identify the subject throughout the clinical study and must be used on all study documentation related to that subject. The subject identification number must remain constant throughout the entire clinical study; it must not be changed at the time of rescreening, enrollment, or randomization. This number will not be the same as the randomization number assigned for the study. Screening procedures/tests may be repeated and reevaluated per Investigator discretion and sponsor approval.

The unique study identification number will consist of 7 digits. The first 3 digits will represent the last 3 digits of the protocol number (e.g., 202). The 4th digit will be an alphabet representing the site code (i.e., site number for the first center is A, site number for the second center is B) and will be identical for all subjects at the same site. The next 3 digits will be assigned in sequential order as subjects are screened (e.g., 001, 002, 003). For example, the first subject to enter screening at site A will receive the number 202A001, and the second subject at the same site will be 202A002.

Treatment Assignment

Subject eligibility will be established at the conclusion of the baseline evaluations, and subjects will then be randomized in a double-blind fashion. The proposed dose design for the current study is for subjects to be randomized in a 1:1:1 fashion into one of three treatment groups (placebo, 35 mg REMD-477, or 70 mg REMD-477).

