Enrollment will take place at 7 to 8 centers in North America. A blinded central randomizer identified by REMD Biotherapeutics will be used to assign the randomization number for all subjects randomized into this study. The unblinded pharmacist or designee at each of the

sites will prepare study drug according to the randomization schedule.

Randomization

Randomization to placebo, 35 mg REMD-477, or 70 mg REMD-477 will be based on a randomization schedule prepared by the CRO's designated unblinded biostatistician and provided to each of the unblinded site pharmacist or designee before the start of the study.

Subjects will be considered randomized once a unique subject randomization number has been assigned. Randomization of a subject may occur within a day prior to Day 1, after subject's eligibility has been confirmed.

After subjects have completed the screening procedures and are confirmed to be eligible for the study, they will be assigned a 5-digit randomization number based in the sequential order in which they met eligibility. The 5-digit randomization number will follow the convention SRXXX, where S is the site code (A, B, C, D, E, F, G, or H), R is a replacement number (with the initial subject to be marked as "0"), and XXX is a sequential randomization number from 001 to 075 for Part A of the Protocol, and 101 to 175 for Part B of the Protocol.

In the event subjects are randomized, but are withdrawn before receiving study medication, a replacement subject may be enrolled in the subject's place and assigned to receive the identical treatment as the replaced subject. The replacement subject will receive a randomization number that is identical to the replaced subject, except that the number '1' will be added to replace "0" in the thousands place of the 5-digit randomization number (e.g., subject A₁001 replaces subject A₀001).

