- A treatment-related Grade 3 or greater adverse event (other than AST or ALT increase as described above) is noted by the Investigator.

If any of the above stopping rules are met the following action(s) should be taken:

1. Stop dosing and convene a Safety Review Committee meeting;
2. Review AE for evidence of relationship to treatment;
3. Consider unblinding, as appropriate*;
4. May resume enrollment and continue the study if recommended by the Safety Review Committee.

**A subject's treatment assignment should only be unblinded when knowledge of the treatment is essential for the further management of the subject, or may impact the safety of subjects currently enrolled.*

Concomitant Therapy

Throughout the study, the Principal Investigator may prescribe concomitant medications or treatments deemed necessary to provide adequate medical care.

For subjects enrolled in this study, the allowable concomitant medications include insulin, angiotensin converting enzyme inhibitors, angiotensin receptor blockers, beta adrenergic receptor blockers, calcium channel blockers, diuretics, HMG-CoA reductase inhibitors, fibrates, low-dose aspirin, NSAIDs, and hormone replacement therapies (estrogen or thyroid). Subjects on an SGLT2 inhibitor should discontinue the SGLT2 inhibitor during the Screening period, at least 2 weeks prior to the start of the Lead-in Period. The use of any other concomitant medication requires Investigator's discretion and must not interfere with the study outcomes. Doses of allowable concomitant medications must be stable for > 1 month prior to Day 1.

Any use of concomitant therapy or treatments will be recorded in the applicable eCRF page with appropriate source documentation.

Proscribed Therapy during Study Period

Current or recent (within 1 month of screening) use of diabetes medications other than insulin, or use of other medications that are known to affect the outcome measures are prohibited for this study.

No other medication (with the exception of those listed above) is to be taken within 2 weeks or 5 half-lives (whichever time period is greater) before Day 1 and through the duration of the study. All herbal or nutritional supplements are subject to investigator's discretion.

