10. STATISTICAL CONSIDERATION

Study Endpoints, Subsets, and Covariates

Primary Endpoints:

- Change from baseline at Week 12 in daily insulin use.

Secondary Endpoints:

- Change from baseline at Week 13 in fasting glucose and glucose AUC after the MMTT – for Part A only.
- Change from baseline at Week 12 in average daily 24-h blood glucose concentration and time within target range as assessed by CGM and seven-point glucose profile.
- The product of the ratio of average glucose (Week 12/Baseline) and ratio of average insulin use (Week 12/Baseline).
- Subject incidence of adverse events and clinically relevant changes in medical history, physical examination, laboratory safety values, and ECGs.
- Incidence of hypoglycemic events.
- Change from baseline at Week 13 in HbA1c.
- Proportion of subjects who achieve HbA1c reduction of $\geq 0.4\%$.
- Change from baseline at Week 13 in fasting C-peptide and C-peptide AUC after MMTT and arginine challenge (for a subset of subjects who were enrolled prior to Protocol Amendment #1) – in Part A only.
- Change from baseline at Week 13 in peripheral levels of fasting glucagon, active and total glucagon-like peptide 1 (GLP-1), and glucagon and GLP-1 (active and total) AUC after MMTT challenge – in Part A only.
- REMD-477 plasma concentrations and incidence of anti-REMD-477 antibody formation.

Exploratory Endpoints:

- Change from baseline at Week 13 in body weight.
- Change from baseline in QOL score at week 13.
- Changes in intrahepatic lipid content as measured by MRI-PDFF (for a subset of subjects in Part B only)
- Changes in intrahepatic lipid content as measured by FibroScan® (for a subset of subjects in Part B only)

Sample Size Considerations:

The power calculation for the primary endpoint (difference in the change from baseline in daily insulin use) is based on the assumption that daily insulin requirement will not change in the placebo group and will decrease in the REMD-477 treatment group. Based on expected coefficient of variation of the daily insulin requirement of ~36%, it is estimated that ≥ 22 subjects in each group (treatment and placebo) will be sufficient to detect a difference of at least 30% with a power of 0.8, and an alpha value of 0.05. To ensure statistical power, and to avoid inadequacy due to unanticipated subject dropout, an N=25/group is used for each part of this study.

Access to Individual Subject Treatment Assignments

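### Protocol Section 8 gives the replacement for a dosed subject that subject's arm, so if the first subject's arm has become known, the replacement's arm is known before enrolment

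*Protocol*

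**What the plan says.** Two parts of the protocol deal with replacement.

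- **Section 5** covers subjects who never took study drug: "if a subject has been randomized and does not receive study drug, the subject may be replaced". The Randomization text there gives the replacement the identical treatment and a number that changes only in the replacement digit.
- **Section 8** restates that case and adds a second: "Subjects who receive study drug and do not complete all study procedures as per protocol may be replaced". For both it sets the same rule: "A replacement subject will be assigned the same dose, route, and treatment group of the replaced subject". For "subjects who are removed from the study as a result of investigational drug related or possibly related adverse events", replacement is left to the Investigator's discretion.

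Section 3 (Number of Subjects) says in general terms that the Principal Investigator or the sponsor may decide to enrol replacements.

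On unblinding, Sections 10 and 11 allow the Principal Investigator, the medical monitor or the clinical operations director to break a subject's blind when management of that subject or the safety of enrolled subjects requires it. Section 6 lists the actions to take when an individual stopping rule is met. These include convening the Safety Review Committee and "Consider unblinding, as appropriate".

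The SAP does not mention replacement subjects.

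**The concern.** A replacement who inherits an arm is concealed only as well as the subject replaced. If that subject's arm is known to the person who decides on replacement, that person knows what the next subject will receive before choosing whom to enrol, and still knows it throughout follow-up.

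The primary endpoint makes this matter. Daily insulin use is set by subjects titrating to glucose targets, and the investigator may adjust the doses (Section 7). Research staff coach insulin dosing by telephone after Doses 1 and 2. In Part A the investigator may also allow an insulin reduction on the day of randomisation for subjects with lower screening HbA1c. Knowing the arm could influence any of these decisions, and so the Week 12 value itself.

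**Working it through.** **1. The plan's own figure.** The claim does not depend on the sample size. The figure matters only for whether the trial can do without replacing dosed subjects. Inputs from Protocol Section 10: coefficient of variation 36% (used as the SD), difference 30%, power 0.80, alpha 0.05. Sidedness is not stated; two-sided is assumed.

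- n per group = 2 × [(1.960 + 0.842) × 36/30]² = 22.6, rounded up to 23. The protocol states 22.
- Power at 22 = Φ(30 / (36 × √(2/22)) − 1.960) = Φ(2.764 − 1.960) = 0.789. Power at 25 is 0.838.
- With the t distribution, n = 23.6, rounded up to 24. Power is 0.770 at 22 and 0.823 at 25.

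The stated figure reproduces closely. The dropout allowance in 25 per group is 1 − 22/25 = 12% on the protocol's figure, 1 − 23/25 = 8% on the normal recalculation, and 1 − 24/25 = 4% on the t-based one.

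**2. Does the arm pass on?**

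| | Who may be replaced | What the replacement inherits |
|---|---|---|
| Section 5 | Undosed subjects | Identical treatment; same number apart from the replacement digit |
| Section 8 | Undosed subjects and dosed non-completers | Dose, route and treatment group; number not mentioned |

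So the arm passes on for dosed subjects too.

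**3. Can the first arm become known to whoever decides?** There are three documented routes.

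- The Principal Investigator may break the blind, and may also decide on replacement.
- The Safety Review Committee includes the site Investigators, the medical monitor and the clinical operations director. Its review is blinded unless unblinding is judged necessary. A stopping event convenes it with unblinding on its list of actions.
- Sponsor study teams may be unblinded for the preliminary analyses after the 30th and 60th subjects complete Day 85 (Protocol Section 10, SAP Section 11), and the sponsor may also decide on replacement. The documents do not say whether the same people hold both roles.

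**4. Do the safeguards cut the link?** The central randomiser and the bar on site access to the schedule and pharmacy records protect the list. Here the knowledge would come from a code break combined with the inheritance rule, which neither safeguard touches. Neither document bars replacing an unblinded subject, gives the replacement a fresh code, or provides for hiding from the site which subject is being replaced.

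**5. How predictable is the arm?**

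- Fresh code under 1:1:1: about 1/3 chance of a correct guess (block size is not given).
- Inherited arm, once the first subject's arm is known: 1.

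**6. How often?** The number affected is the number of dosed subjects who are unblinded to a decision-maker and then replaced in the same arm. The documents give neither an unblinding rate nor a replacement rate, so no count follows.

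**The case against.** The strongest reply is that several things must all happen. A code break must reach the decision-maker, although unblinding for reasons other than subject management or safety is a protocol violation. A discretionary replacement must then follow. Without a code break, the inherited arm is as concealed as any other. Inheritance also keeps the arms at 1:1:1. All of this stands, and it limits the point to a conditional one. It does not remove it, because once the condition is met nothing in the plan restores concealment.

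A reader might infer more than the documents support:

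- **That the number gives the replacement away.** The rule "The replacement subject will receive a randomization number that is identical to the replaced subject" applies to this case: "In the event subjects are randomized, but are withdrawn before receiving study medication". Section 8 does not extend it to dosed subjects. The point needs only the shared arm.
- **That regulatory unblinding of serious, unexpected, related events is a further route.** Section 9 has the sponsor or CRO do this before submission and does not send the result to the site.
- **That a liver-enzyme stop reveals active drug.** Section 2 reports that transaminase rises in the type 2 diabetes study came without bilirubin or alkaline phosphatase increases. It does not describe any as meeting either liver stopping criterion. Such a stop would also not separate 35 mg from 70 mg.
- **That replacement enriches an arm with subjects who tolerate the drug.** If the blind holds, a replacement is a new draw from the same eligible population.
- **That Sections 5 and 8 conflict.** Section 5 permits replacement of undosed subjects without saying that only they may be replaced. Section 8 adds to it.

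**Conclusion.** The point holds in conditional form. When a dosed subject's arm has become known to the Principal Investigator or to the sponsor staff who decide on replacement, and that subject is replaced under Section 8, the replacement's arm is certain before enrolment instead of a guess of about 1 in 3. It rests on Section 8 being applied as written and on the code-break result reaching the decision-maker.

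It does not follow that the blind fails for replacements in general, and the documents do not show that any such case has occurred. No share of subjects can be put on it. It is a foreseeable and avoidable gap in concealment that a small change would close, not a defect that undermines the trial.

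**What to change.** 1. **Protocol Section 8.** Remove replacement of dosed subjects. The protocol already says of its sample size: "to avoid inadequacy due to unanticipated subject dropout, an N=25/group is used for each part of this study". Section 8 also asks subjects who stop study drug to continue scheduled observations, so replacement is not the only way to obtain Week 12 data. If replacement of dosed subjects is kept, state at minimum that no unblinded subject is replaced in the same arm.
2. **Protocol Sections 5 and 8.** Give any replacement the next unused code on the randomisation schedule, not the replaced subject's arm. Codes now run 001 to 075 for Part A and 101 to 175 for Part B, so the list needs a few more per Part. For Part A, 076 to 099 are free under the present numbering.
3. **SAP Section 9.** State that every dosed subject, replaced or replacement, is analysed in the assigned arm.

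The cost is a short amendment, a slightly longer list, arm sizes that may differ by one or two, and slightly fewer completers. Because the recalculated dropout allowance is 4% to 8% rather than 12%, a sponsor worried about completers can use the extra codes to randomise a few more subjects, which keeps concealment intact.

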9. SAFETY DATA COLLECTION, RECORDING, AND REPORTING

Adverse Events

An adverse event is defined in the International Conference on Harmonisation (ICH) Guideline for Good Clinical Practice as “any untoward medical occurrence in a patient or clinical investigation subject administered a pharmaceutical product and that does not necessarily have a causal relationship with this treatment.” (ICH E6:1.2)

This definition of adverse events is broadened in this study to include any such occurrence (e.g., sign, symptom, or diagnosis) or worsening of a pre-existing medical condition from the time that a subject is admitted to the clinical research unit, CRU, for the Overnight Baseline Visit or returns to the CRU for the Baseline Visit.

This definition of adverse events also includes worsening of a pre-existing medical condition. Worsening indicates that the pre-existing medical condition (e.g., cancer, diabetes, migraine headaches, gout) has increased in severity, frequency, or duration of the condition or an association with significantly worse outcomes.

Interventions for pretreatment conditions (e.g., elective cosmetic surgery) or medical procedures that were planned before study enrollment are not considered adverse events.

The Principal Investigator is responsible for reviewing laboratory test results and determining whether an abnormal value in an individual study subject represents a change from values before the study. In general, abnormal laboratory findings without clinical significance (based on the Principal Investigator's judgment) should not be recorded as adverse events; however, laboratory value changes requiring therapy or adjustment in prior therapy are considered adverse events.

Serious Adverse Events

A serious adverse event (SAE) is defined as an adverse event that:

- is fatal
- is life threatening (places the subject at immediate risk of death)
- requires in-patient hospitalization or prolongation of existing hospitalization
- results in persistent or significant disability/incapacity
- is a congenital anomaly/birth defect
- other significant medical hazard

A hospitalization meeting the regulatory definition for “serious” is any inpatient hospital admission that includes a minimum of an overnight stay in a health care facility. Any adverse event that does not meet one of the definitions of serious (e.g., emergency room visit, outpatient surgery, or requires urgent investigation) may be considered by the investigator to meet the “other significant medical hazard” criterion for classification as a serious adverse event.

Reporting Procedures for All Adverse Events

The Principal Investigator is responsible for ensuring that all adverse events observed by the Principal Investigator or reported by subjects are collected and recorded in the subjects' medical records, in the eCRF, and, for serious adverse events, on the serious adverse event report (SAER) form. These adverse events will include the following:

- All serious adverse events that occur after the subject has signed the informed consent form.
- All non-serious adverse events that occur after treatment with investigational product.

The following adverse event attributes must be assigned by the Principal Investigator: adverse event diagnosis or syndrome(s) (if known, signs or symptoms if not known); event description (with detail appropriate to the event); dates of onset and resolution; severity; assessment of relatedness to investigational product; and action taken. The Principal Investigator may be asked to provide follow-up information, discharge summaries, and extracts from medical records or eCRF pages.

If applicable, the relationship of the adverse event to the investigational product will be assessed by means of the question: “Is there a reasonable possibility that the event may have been caused by the investigational product (i.e., cannot be ruled out)?” The Principal Investigator should respond to this question with either Yes or No.

If a serious adverse event occurs before randomization to investigational product, the relationship of the adverse event to study screening is to be assessed by means of a similar question: “Is there a reasonable possibility that the event may have occurred because of study related activity or procedure?” The Principal Investigator should respond to this question with either Yes or No. If the answer is “Yes”, record what activity or procedure is suspected.

The CTCAE V. 4.03 will be used in this study.

Medically significant adverse events considered related to the investigational product by the Principal Investigator or the sponsor will be followed until resolved or considered stable.

It will be left to the Principal Investigator's clinical judgment to determine whether an adverse event is related and of sufficient severity to require the subject's removal from treatment or from the study. A subject may also voluntarily withdraw from treatment due to what he or she perceives as an intolerable adverse event. If either of these situations arises, the subject should be strongly encouraged to undergo an end-of-study assessment and be under medical supervision until symptoms cease or the condition becomes stable.

Adverse Event Severity Grade

Each adverse event must be assigned a Grade, which refers to the severity of the adverse event. The CTCAE v4.03 displays Grades 1 through 5 with unique clinical descriptions of severity for each adverse event on this general guideline:

- Grade 1 – Mild AE
- Grade 2 – Moderate AE
- Grade 3 – Severe AE
- Grade 4 – Life-threatening or disabling AE
- Grade 5 – Death related to AE.

Serious Adverse Event Reporting Procedures

Serious adverse events will be collected throughout the study period, beginning with the signing of the informed consent through 30 days after the last dose of investigational product or end of the study (including the follow-up period), whichever is longer. Serious adverse events also will be collected if they occur >30 days after the last dose of investigational product or after the end of the study AND is thought to be possibly related to investigational product.

All serious adverse events must be reported to REMD Biotherapeutics or designated CRO within 24 hours of discovery or notification of the event. Initial serious adverse event information and all amendments or additions must be recorded on a Serious Adverse Event Report Form and faxed to REMD Biotherapeutics or designated CRO. Relevant medical records should be faxed to REMD Biotherapeutics or designated CRO as soon as they become available; autopsy reports should be provided for deaths if available.

To comply with local or regional serious adverse event reporting regulations, the treatment assignment of subjects who develop serious, unexpected, and related adverse events may be unblinded before submission to regulatory authorities by REMD Biotherapeutics or designated CRO. Determination of expectedness for REMD Biotherapeutics or designated CRO will be based on the contents of the Investigator's Brochure for investigational products.

If a subject is permanently withdrawn from the study because of a serious adverse event, this information must be included in the initial or follow-up Serious Adverse Event Report Form as well as the End of Study eCRF page.

The Principal Investigator should notify the appropriate IRB or ethics committee of serious adverse events occurring at the CRU and other adverse event reports received from REMD Biotherapeutics or designated CRO, in accordance with local procedures and statutes.

